All study data will be kept identified by a study ID number. The file linking the participant ID number and identifying information of the individual (name, contact information) will be stored in a locked cabinet in Moshi, Tanzania. The Duke study team will not have access to that file.

5. Trainee Supervision

The research team at KCMC, led by the Co-PI, [name], will be involved with orientation, training and supervision of students and trainees involved in the study. This will be done with the support of the study team at Duke University. The KCMC team will also provide the trainees with resources needed to facilitate their involvement in the project(s) (e.g., workspace, equipment, access to data, etc.), meet regularly with them to provide support, guidance, and feedback and communicate with the Duke team to provide feedback on their progress.

6. Compensation

Below we describe the compensation procedures that KCMC will use for participants by study phase. Under all circumstances, participants who begin a procedure will receive compensation, even if they voluntarily choose not to complete the procedure.

Phase 1: Key Informant Interviews with Health Care Providers

Compensation: Participants will receive a small gift valued at 5,000 TSh (~3 USD) for participation. With the guidance of the Ministry of Health, it was determined that compensation in the form of a gift would be more appropriate than cash.

Phase 2: Surveys and In-depth Interviews with female patients

Compensation: Participants will receive 5,000 TSh (~3 USD) for participation in each survey assessment and in-depth interview.

Phase 3: Focus Group Discussions and In-Depth Interviews with Stakeholders

Compensation: Patients will receive 5,000 TSh (~3 USD) for participation, and providers will receive an equivalently valued gift for participation.

Phase 4: Medical Record Review

No human subjects to compensate.

Phase 5: Development of the *Maisha* Intervention

Compensation: Trial run participants will receive 10,000 TSh (~6 USD) per visit for participation. Cognitive interview participants will receive 5,000 TSh (~3 USD) for their participation.

Phase 6: Pilot RCT of the *Maisha* Intervention

Compensation: No compensation will be offered at baseline, but nutritious snacks will be given to all women taking part. Women who attend a follow-up counseling session will receive 5,000 TSh (~3 USD) to cover their transportation. Women who complete a 3-month survey will receive 5,000 TSh for their participation, and snacks will be offered during the assessment. Women who complete an in-depth interview will receive an additional 5,000 TSh.

7. Informed Consent

Prior to participating in the study, KCMC staff and the Duke graduate student will obtain informed consent from participants. A KCMC research assistant and the Duke graduate student will describe the study in detail to the participant, allow him/her ample time to read the consent form thoroughly (or have it read to them) and ask questions, and ensure that he/she understands the purpose of the study, study procedures involved, and potential risks. Verification of comprehension of informed consent will be accomplished by asking participants to recall central points in the consent process. This procedure will also provide an opportunity to clarify any points of confusion. Participants will complete a separate informed consent for observations of their medical care at the clinic. Participants will sign one copy of the informed consent form and will be given a copy for their

personal records. If the participant is not able to write his/her name, a thumb print can be used in lieu of a signature. Participants will be told at enrollment that their decision to participate or not will in no way affect their current or future employment or health care at the facility.

8. Deception

N/A. This study does not involve deception.

9. Debriefing

N/A. Because this study does not include deception, it is not necessary to conduct debriefing (defined by the IRB as telling the subjects about the deception).

10. Statistical analysis

Data analysis for Aim 3 (pilot trial) will follow guidelines of the CONSORT 2010 statement, as extended to pilot feasibility trials.

Feasibility and acceptability of the intervention and the associated trial will be described by: recruitment and retention patterns, participant satisfaction, fidelity, and implementation cost. Retention will be monitored to calculate the percentage of participants who attend the 1-week *Maisha* session (in intervention) and the 3-month assessment, to document barriers to attendance for participants, and to examine differences between those who attend and those who do not. Participant satisfaction data at the 3-month follow-up will be described, with >80% satisfaction used as a metric of acceptability. Qualitative data will be thematically coded for focus on participants' perceptions of the intervention, suggestions for changes, and feasibility moving forward. The fidelity to the intervention will be assessed by examining the percentage of components from the manualized content that are covered in each session. To estimate the cost of the intervention, we will track the time for training and delivery, as well as actual costs incurred. Qualitative feedback and QA data will be used to revise and improve the curriculum for the future.

Potential efficacy will be examined by analyzing separate outcomes for HIV-infected and HIV-uninfected women. For HIV-infected women, we are interested in differences between conditions in health outcomes (retention in PMTCT, medication adherence, depression) and stigma (anticipated stigma, internalized stigma and HIV disclosure). For HIV-uninfected women, we are interested in differences between conditions in stigma (attitudes to PLWH and anticipated stigma), as well as willingness to test for HIV in the future. For outcomes where there is a baseline measure, mixed-effects regressions will be used to model pre-post differences within and between arms, using a time by condition model specification (time, condition, and time*condition). Individual-level random intercepts will be used to account for correlation due to repeated measurement. Using a mixed-effects regression approach leaves flexibility to control for baseline outcome values that may not be balanced between groups due to small sample size, and may improve precision of treatment effect estimation. For outcomes where there is no baseline measure, we will examine differences in means or proportions with 95% confidence intervals. If we suspect, a priori, that baseline imbalance in prognostic covariates may be an issue, we will move into a regression framework. Results across outcomes will generate parameter estimates and potential ranges of values to estimate power for a future R01. This analytic approach is consistent with best practices for analysis of pilot feasibility trials. Data analysis will be led by the KCRI statistician and DGHI postdoc. To reduce bias and ensure reproducibility of results, we will discuss analytic approaches and review syntax as a team. All outcome analysis will be reviewed by an external statistician with study condition blinded (see letter from DGHI Research Design Core).

References

1. U.S. Department of State. *PEPFAR blueprint: Creating an AIDS-free generation*. Washington: U.S. Department of State; 2012.
3. Bateman C. Much ado over the new South African PMTCT guidelines. *S. Afr. Med. J.* Apr 2013;103(4):218-221.

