Aim #4: Conduct a pilot randomized controlled trial (RCT) of *Maisha* to examine 1) feasibility and acceptability in an ANC setting, and 2) impact on early retention in PMTCT, HIV disclosure, and constructs of HIV stigma. *Methods:* We will conduct a pilot RCT with 150 women, both HIV-infected (n=25 *Maisha*; 25 Standard of Care, SoC) and HIV-uninfected (n=50 *Maisha*; 50 SoC). Women will be randomized to receive either the SoC HIV testing and counseling, or SoC plus the *Maisha* intervention. Participants will complete a baseline survey and a follow-up survey at 3 months. Surveys will include measures for health outcomes (e.g., HIV care engagement, adherence to ART, depression, HIV testing), stigma outcomes (e.g., anticipated stigma, enacted stigma, internalized stigma), and other secondary outcomes or potential covariates (e.g., partner support, attitudes to ART, intimate partner violence). A subset of 15 HIV-infected intervention patients will participate in a qualitative in-depth interview at 3 months to provide feedback on the intervention. Clinical data will be abstracted from the medical records of participants completing the 3-month survey.

Overview and timeline

This 5-year study (2016-2021) seeks to understand and inform the implementation of the Option B+ protocol for PMTCT care in the Kilimanjaro Region of Tanzania, and develop an intervention to support women who are newly pregnant and being tested for HIV. The work is being completed in diverse clinical settings, using a multi-methods approach informed by the Consolidated Framework for Implementation Research (Table 1).

Table 1: Study timeline

AIMS	METHODS	YEAR 1				YEAR 2				YEAR 3				YEAR 4				YEAR 5				
		1	2	3	4	1	2	3	4	1	2	3	4	1	2	3	4	1	2	3	4	
Aim 1: Examine implementation of B+ for postpartum care engagement	Observations to assess services and fidelity to protocol																					
	Key informant interviews to assess process and barriers																					
	Record review to assess care engagement outcomes (n=512)																					
Aim 2: Identify factors that impact postpartum care engagement	Enroll pregnant women on ART at clinic sites (n=200)																					
	Follow-up interviews at 3m and 6m postpartum with possible additional surveys up to 2 years postpartum																					
	In-depth interviews to explore care engagement process (n=24)																					

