Aim 3: Identify opportunities to promote postpartum care engagement under B+	Stakeholder feedback meeting & dissemination																					
	Focus group discussions and in-depth interviews with stakeholders at each site																					
	Conduct clinic interviews & observations; refine measures																					
	Analyze data, prepare draft curriculum & record video																					
	Trial run; feedback from advisory board & FGDs; refine & revise																					
Aim 4: Pilot test	Finalize the pilot study protocol																					
	Recruit, baseline & deliver intervention vs. SoC																					
	Conduct 3-month follow up with participants (n=50 HIV+ & 100 HIV-)																					
	Analyze data, write manuscripts & prepare R01																					

Setting

The research will be conducted in diverse clinical sites in the Moshi region that provide PMTCT services. Those sites will be identified in consultation with the Ministry of Health, considering both patient load and capacity to absorb research.

Study procedures by phase

Phase 1: Observations and key informant interviews

First, the KCMC team and the Duke graduate student will conduct *semi-structured observations* in relevant clinical areas in order to document the process of implementing the national PMTCT protocol to promote postpartum HIV care engagement. Observations will include a review of protocols, practices and record keeping procedures. Observations will focus on the services specifically meant to promote engagement in HIV care for women in the postpartum period (e.g., counseling across the perinatal continuum, monitoring of patient retention, transfer of care from antenatal care to reproductive & child health to HIV care & treatment). Following informed

consent specific to clinic observation, the observations will be conducted by a KCMC staff member and the Duke graduate student, who will spend approximately 5 weeks conducting observations on clinic days, using a combination of checklists and ethnographic observation tools.

[figure not shown]

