- *6 months postpartum*: Complete the second survey at approximately 6 months after the birth of the child. Blood samples for viral load testing will also be collected at this time point.
- *Up to 2 years postpartum*: As study resources allow, we will contact participants up to 24 months postpartum to repeat the survey measure.
- *Death of child*: In the event of the death of the child, complete brief research form.

Figure 2: Conceptual model guiding cohort measures

Patient-level data will be collected for the purpose of identifying factors that should be addressed in implementation. All assessments will include questions about demographics and key constructs reflecting intrapersonal issues (e.g., mental health and self-efficacy for ART care), interpersonal issues (e.g., disclosure and social support), and facility-related issues (e.g., knowledge of B+ protocol, perceptions of care quality, care experiences at different clinics). The survey will be conducted in a private room and will take approximately 90 minutes.

Measured predictors will correspond to patient-level factors that reflect individual constructs, interpersonal relationships, and experiences with the health care facility (Figure 2) that may influence care engagement. These predictors were chosen based on meaningful influences that have been identified in prior research. The outcome of interest, postpartum HIV care engagement, will include receipt of ART (confirmed by clinical record review) and self-reported ART adherence with the ACTG adherence instrument,⁴⁷ using strategies to improve recall and validity.⁴⁸ We will implement mechanisms for retention (as [name] has done for IMPAACT study). For women who are lost from the study, their care engagement data will be extracted from medical records.

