For the full pilot test of *Maisha*, female ANC patients who are interested in enrolling in the study will be orally administered the informed consent by the study researcher. Participants will then complete an interviewer-administered, structured baseline survey. The survey will include questions about demographics, social support, attitudes toward HIV and people living with HIV, HIV testing history, and mental health. Following the baseline survey, participants will be randomized to receive either the control condition (standard of care) or the intervention condition (standard of care + *Maisha*) (Figure 4).

Participants assigned to the control condition will receive the standard of care at the clinic, which includes all standard procedures related to HIV counseling.

Participants assigned to the intervention condition will receive the *Maisha* Session 1 counseling intervention (video, followed by a brief counseling session) immediately following the baseline survey, in the same private meeting space. They will then return to the waiting area to await the standard of care for the first ANC visit (which includes HIV testing). At this time, the study researcher will inform the clinic nurse that the participant is a part of the intervention condition.

Upon completion of the standard of care HIV counseling and testing, participants who are HIV-positive will be escorted by clinic nurses back to the study researcher's office to immediately complete the *Maisha* Session 2 counseling session. At the conclusion of this session, the participant will be invited and encouraged to attend a Session 3 individual counseling session at the same location 1 week later.

3 months after baseline, all HIV-positive participants (expected n=50) and a sub-set of 100 HIV-negative participants will complete a follow-up survey. The survey will explore key constructs reflecting health outcomes (HIV care engagement, adherence to ART, mental health), stigma outcomes (internalized, anticipated, and enacted stigma), and secondary outcomes (social support, partner support, intimate partner violence). This survey will be conducted in a private room and will take approximately 60 minutes.

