Immediately after the 3-month survey, a subset of 15 HIV-positive intervention participants (5 established diagnoses, 10 new diagnoses) will be invited to participate in a qualitative in-depth interview (IDI) to explore their reactions to the intervention with greater nuance. Interviews will be conducted immediately after the survey and will take an additional 60 minutes. The IDI will be conducted in Kiswahili, using a semi-structured guide. Interviews will be audio recorded with participants' permission.

At the conclusion of pilot trial participation, the research nurse will review the medical records of the 150 pilot trial participants who are selected to receive follow-up as part of the study. A structured data extraction form will be used to record key data on HIV care engagement.

2. Subject Selection

Below are the eligibility and recruitment procedures that the KCMC team will use for inclusion of participants by study phase.

[figure not shown]
Phase 1: Key Informant Interviews with Health Care Providers

Eligibility: 30 health care providers: Individuals who are employed at one of the three study clinics and are involved in the care of HIV-infected women who are pregnant or postpartum. These individuals may include nurses, counselors, physicians, data capturers, and managers.

Recruitment: For health care providers, the KCMC PI ([name]), the Duke graduate student and KCMC research nurses will conduct a brief presentation at each of the study clinics. The research nurse and the Duke graduate student will then approach providers individually to invite them to participate in a key informant interview.

Phase 2: Surveys and In-depth Interviews with female patients

Figure 4. Pilot test design
1st ANC appointment

Eligibility: 200 female patients: Women who are ≥ 18 years of age, diagnosed with HIV, prescribed ART, and pregnant at the time of enrollment are eligible to enroll. Participants may either be newly initiating ART during pregnancy, or continuing ART due to an established HIV diagnosis. To ensure the safety of participants and integrity of the data, participants will be excluded if the attending physician determines that the patient has impaired mental status.

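### Aim #4 gives 150 as the size of the randomised trial, but Phase 6 implies about 1,000 women randomised and 150 selected for follow-up; the two places also define the record-abstraction set differently

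*Combined protocol and SAP*

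**What the plan says.** **Size of the trial.** Section 1, Aim #4: "We will conduct a pilot RCT with 150 women", divided into 25 and 25 HIV-infected and 50 and 50 HIV-uninfected. The next sentences say that the women are randomised and that participants complete surveys at baseline and 3 months.

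The Phase 6 procedure in section 1 puts randomisation early: "Following the baseline survey, participants will be randomized to receive either the control condition". HIV testing comes later in the same visit. Of intervention women who have finished Session 1 it says: "They will then return to the waiting area to await the standard of care for the first ANC visit (which includes HIV testing". Section 2, Phase 6, gives 1,000 female patients. It stops enrolment at 50 HIV-infected women and expects about 1,000 women to give consent and complete baseline before that number is reached.

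Three places present 150 as a follow-up number:
- Table 1, Aim 4 row: "Conduct 3-month follow up with participants (n=50 HIV+ & 100 HIV" (the last group being the HIV-negative women).
- Phase 6: "all HIV-positive participants (expected n=50) and a sub-set of 100 HIV-negative participants will complete a follow-up survey".
- Phase 6, record review: the 150 are those selected to receive follow-up.

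**Record abstraction.** Aim #4 ends: "Clinical data will be abstracted from the medical records of participants completing the 3-month survey". Phase 6 says that the research nurse will "review the medical records of the 150 pilot trial participants who are selected to receive follow-up as part of the study", to record data on HIV care engagement. Section 10 lists retention in PMTCT among the health outcomes for HIV-infected women. It also plans to compare women who attend with those who do not.

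**The concern.** A reader of Aim #4 takes 150 as the number randomised, the number followed and the denominator for retention. On the Phase 6 figures the first of these differs from the other two by a factor of nearly seven. Section 10 makes recruitment and retention patterns feasibility outcomes, so the protocol should say which number is which.

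The record sentence could affect a result. Women who drop out of care may also be harder to bring back for a survey. If records were abstracted only for women who came back, a measure of staying in care would be conditional on something that may be related to staying in care. Phase 2 of the same protocol avoids this for its own cohort: "For women who are lost from the study, their care engagement data will be extracted from medical records".

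**Working it through.** **1. What 150 reproduces.** Aim #4: 25 + 25 + 50 + 50 = 150. Table 1 and Phase 6: 50 + 100 = 150. The figure reproduces exactly as the follow-up set.

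**2. How many are randomised.** Inputs: about 1,000 women at baseline (section 2, Phase 6), and randomisation after baseline with no further selection step described (section 1, Phase 6). Together these give about 1,000 randomised. No single sentence states this, and Figure 4 is not shown, so it is a derivation from the text.
- HIV-infected: 50, an implied prevalence of 50/1,000 = 5%.
- HIV-uninfected: 1,000 − 50 = 950.
- Share of randomised women selected for follow-up: 150/1,000 = 15%.
- Share of HIV-uninfected women selected: 100/950 = 10.5%.
- HIV-uninfected women with no planned 3-month survey: 950 − 100 = 850.

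The conclusion does not hang on the 1,000. At assumed prevalences of 3% and 8%, finding 50 HIV-infected women takes 50/0.03 = 1,667 and 50/0.08 = 625 women, both well above 150.

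**3. What the denominator does.** If all 150 selected women returned, 3-month retention would be 150/150 = 100% of those selected but 150/1,000 = 15% of those randomised.

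**4. The two record sets.** They coincide only if every selected woman completes the survey. At an assumed 80% completion, Aim #4 gives 0.80 × 150 = 120 records (0.80 × 50 = 40 HIV-infected) and Phase 6 gives 150 (50 HIV-infected).

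**5. Possible bias if only completers are abstracted.** Assumptions not in the documents: 30 of 50 HIV-infected women (60%) are truly retained in PMTCT, and L women miss the survey. The figure among completers lies between (30 − L)/(50 − L), if all the missing women were retained, and 30/(50 − L), if none was.

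| L | Lower | Upper | Departure from 60% |
|---|---|---|---|
| 5 | 25/45 = 55.6% | 30/45 = 66.7% | −4 to +7 points |
| 10 | 20/40 = 50.0% | 30/40 = 75.0% | −10 to +15 points |

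There is no bias if missing the survey is unrelated to retention in care.

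**6. Between arms, same kind of illustration.** Let 15 of 25 be retained in each arm (true difference 0), with 1 woman missing the survey in one arm and 5 in the other. If all six were not retained, the result is 15/24 = 62.5% against 15/20 = 75%, a difference of 12.5 points. If the one woman was retained and the five were not, it is 14/24 = 58.3% against 75%, or 16.7 points. If the one was not retained and the five were, it is 62.5% against 10/20 = 50%, or 12.5 points the other way. For scale, the 95% half-width for a difference at 60% with 25 per arm is 1.96 × √(2 × 0.6 × 0.4/25) = 0.27, about 27 points.

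**The case against.** Aim #4 is a summary, and the operative text is already right. Section 2 gives 1,000 women, Phase 6 places randomisation and calls the 100 a sub-set, and its record review covers everyone selected. A reader who gets that far can work out the true size. This stands, and it limits the severity.

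Aim #4 does not say that only completers' records are abstracted. It is written as if all 150 complete both surveys, so its last sentence can be read as shorthand for the 150. That is a fair reading, but the sentence still names a narrower set than Phase 6 does, and section 10 expects some non-attenders. The documents do not define retention in PMTCT or say which source supplies it, and care engagement is also a survey topic. The link from records to that outcome is therefore an inference. The between-arm illustrations also lie within the sampling error of so small a trial.

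A reader might infer three stronger points, which the documents do not support:
- **That about 850 randomised women lose their outcome by mistake.** Phase 6 chooses a sub-set of HIV-uninfected women on purpose.
- **That the trial is too small because no loss is allowed for.** The pilot promises no power, makes 3-month attendance something to be measured, and nowhere claims 50 HIV-infected women analysed.
- **That retention in PMTCT will be overstated.** Upward bias is plausible, but no figure in the documents fixes its direction or size, and it arises only if staff follow Aim #4 rather than Phase 6.

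**Conclusion.** Aim #4 is wrong as written on the size of the trial. About 1,000 women are randomised before HIV testing at that visit, and 150 is the set selected for 3-month follow-up. This rests on reading Phase 6 and section 2 together and on the plan's own estimate of 1,000.

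The record-abstraction sentences in Aim #4 and Phase 6 name different sets and need to be reconciled. The consequence is conditional: a possible bias in a record-based retention or engagement measure, illustrated above under assumed retention and survey loss. Severity is low to moderate. This is a correction to a summary section, with one sentence that could alter a result if it were followed.

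**What to change.** 1. Restate Aim #4 along these lines: about 1,000 women will be randomised before HIV testing; enrolment stops at 50 HIV-infected women (25 per arm expected); all HIV-infected women and a sub-set of 100 HIV-uninfected women (50 *Maisha*, 50 SoC) are selected for 3-month follow-up. Keep the 50/50 split, because Aim #4 is the only place that states it.
2. Report the number randomised separately from the number selected, and name the number selected as the denominator for 3-month retention.
3. Change the last sentence of Aim #4 to agree with Phase 6: records are abstracted for every woman selected for follow-up, whether or not she completes the survey.

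Table 1 and the Phase 6 procedure need no change. The cost is protocol wording, with no added participants or visits. No records are added beyond what Phase 6 already plans; compared with the Aim #4 sentence, the extra records are those of selected women who miss the survey.

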Eligibility: 1000 female patients: Women who are > 18 years of age, pregnant, and attending their first ANC appointments for the current pregnancy at one of the two pilot test study sites are eligible to enroll. To ensure the safety of participants and integrity of the data, participants will be excluded if the attending physician determines that the patient has impaired mental status.

Recruitment: Research staff will work with clinic staff, including the receptionist at the Reproductive & Child Health (RCH) clinic and the ANC clinic nurse-in-charge, to identify women who are eligible for the study. When a woman arrives for her ANC appointment, she is routinely asked whether this is her first clinic appointment for the current pregnancy. For all women who answer “yes” to this question, the intake nurse will inform her that there is a research study taking place and inquire whether she would like to speak to the study researcher. Those who agree will meet with the study researcher, who will explain the study, review eligibility criteria, and offer her the opportunity to participate if she chooses, following the informed consent procedures. Clinic staff will be given a small monthly stipend to compensate for the added work of identifying and referring interested clients to the study staff; they will *not* be reimbursed based on whether or not the referral is successful, so that compensation does not create undue influence on a patient’s participation in the study. Enrollment will stop when we have enrolled 50 women who are HIV infected, which we estimate will require consenting and baselining approximately 1000 women over a six month period.

Compensation: No compensation will be offered at baseline, but nutritious snacks will be given to all women taking part. Women who attend a follow-up counseling session will receive 5000 TSh (~3 USD) to cover their transportation. Women who complete a 3-month survey will receive 5000 TSh for their participation, and snacks will be offered during the assessment. Women who complete an in-depth interview will receive an additional 5000 TSh.

3. Risks and Benefits

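### Aim 4 and Phase 6 differ on whose records are abstracted in the pilot trial, and section 10 gives no source or denominator for retention in PMTCT: a minor inconsistency to reconcile

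*Combined protocol and SAP*

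**What the plan says.** Two places describe the pilot's record review, and a third uses its likely product.

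- **Section 1, Study aims, Aim #4:** "Clinical data will be abstracted from the medical records of participants completing the 3-month survey". The same paragraph names early retention in PMTCT first among the impact outcomes and puts HIV care engagement among the survey measures.
- **Section 1, Phase 6, Procedure:** at the end of participation the research nurse will "review the medical records of the 150 pilot trial participants who are selected to receive follow-up". The next sentence reads: "A structured data extraction form will be used to record key data on HIV care engagement". Earlier in that procedure the follow-up group is set out: at 3 months, "all HIV-positive participants (expected n=50) and a sub-set of 100 HIV-negative participants will complete a follow-up survey". That survey, too, covers HIV care engagement.
- **Section 10:** retention in PMTCT heads the health outcomes compared between conditions for HIV-infected women. No data source or denominator is given. The other retention in section 10 is attendance at the 1-week session and the 3-month assessment, which is a feasibility measure and a different quantity.

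Two further statements matter. Section 10 plans "to examine differences between those who attend and those who do not", so it allows for women who miss the 3-month assessment. It also says what the estimates are for: "Results across outcomes will generate parameter estimates and potential ranges of values to estimate power for a future R01".

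**The concern.** Being selected for follow-up and completing the survey define the same women only if all 150 complete it. Once a selected woman misses the survey, Aim 4 leaves her record out and Phase 6 keeps it in. Nothing in the document says which wording governs.

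Survey completion happens after randomisation and is plausibly related to being in care. If retention were read only among completers, it would be conditioned on something close to the outcome itself. Retention would be overstated if women out of care complete less often, and the difference between arms would no longer be protected by randomisation.

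The silence in section 10 adds a second route to the same result. If retention were taken from the survey, non-completers would be missing whichever record-review wording is followed. For the Phase 2 cohort the protocol says outright that care-engagement data for women lost from the study come from medical records. For the pilot, Phase 6 implies this but no sentence says it.

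**Working it through.** **1. The planned numbers agree.** Aim 4: 25 + 25 HIV-infected and 50 + 50 HIV-uninfected = 150. Phase 6: 50 + 100 = 150. The difference lies only in the condition for abstraction.

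**2. When the wording matters.**

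| Source of retention | Wording followed | HIV-positive women in the estimate |
|---|---|---|
| Records | Phase 6 | All selected women (expected 50) |
| Records | Aim 4, literally | Survey completers only |
| Survey | Either | Survey completers only |

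**3. Effect of conditioning on completion.** Let p be true retention in an arm, a the survey completion among retained women and b that among women not retained. Retention seen among completers is

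p·a / [p·a + (1 − p)·b].

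The documents give none of these rates for the pilot, so all are assumptions. Take p = 60% under standard of care (SoC) and 80% under Maisha, a true difference of 20 points, with the same a and b in both arms. For a = 95% and b = 80%:

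- SoC: 0.57 / (0.57 + 0.32) = 64.0%
- Maisha: 0.76 / (0.76 + 0.16) = 82.6%

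Expected non-completers are 25 × [1 − (p·a + (1 − p)·b)], summed over the two arms.

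| a / b | SoC | Maisha | Difference | Shift | Non-completers of 50 |
|---|---|---|---|---|---|
| 85% / 85% | 60.0% | 80.0% | 20.0 | 0 | 7.5 |
| 95% / 80% | 64.0% | 82.6% | 18.6 | −1.4 | 4.75 |
| 95% / 50% | 74.0% | 88.4% | 14.3 | −5.7 | 9.25 |
| 90% / 30% | 81.8% | 92.3% | 10.5 | −9.5 | 14.0 |

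Differences were taken before rounding. The first row shows that completion unrelated to retention costs numbers but causes no bias.

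**4. Completion that differs by arm.** Assume no true effect (50% retained in both arms), a = 95%, and b = 40% under SoC but 70% under Maisha. Completers show 0.475 / 0.675 = 70.4% against 0.475 / 0.825 = 57.6%, a spurious −12.8 points. Swapping the two values of b gives +12.8. The direction is therefore not fixed.

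**5. Comparison with sampling error.** At the planned 25 per arm and the assumed true rates, the 95% half-width is 1.96 × √(0.6·0.4/25 + 0.8·0.2/25) = 1.96 × √0.016 = 24.8 points. Every shift above is smaller.

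**6. Carry-over to the R01.** Take 80% power, two-sided 5%, and the two-proportion formula n = [1.96·√(2·p̄·(1 − p̄)) + 0.84·√(p₁(1 − p₁) + p₂(1 − p₂))]² / (p₂ − p₁)², where p̄ is the mean of p₁ and p₂. The true rates need 82 per arm. The completer-only rates in the last three rows, taken at face value, would give 88, 116 and 160.

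**The case against.** The strongest reply is that the protocol already has this right where it counts. Phase 6 is the operative procedure: it says who reviews, when, whose records and with what form, and selection for follow-up does not depend on completion. The Aim 4 sentence may be shorthand that separates the 150 from the much larger baselined group, "which we estimate will require consenting and baselining approximately 1000 women over a six month period" being how the Phase 6 eligibility text describes it. Phase 6 also speaks of the selected women as those who will complete the survey, so the authors may have meant one group throughout. This stands, and it is why the point is minor.

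The sizes also rest on assumed gaps in completion between retained and non-retained women. With a 15-point gap (95% versus 80%) the shift is only 1.4 points; the larger shifts need gaps of 45 or 60 points. The trial is a pilot with no stated power claim, and its results are to supply ranges of values. That stands too.

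What does not fall away is that no sentence ranks the two wordings and that section 10 leaves the source open. The planned comparison of attenders with non-attenders would describe selective attendance but would not correct a retention estimate restricted to completers.

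A reader might infer that pilot retention will be estimated in survey completers and so will be biased. The documents do not support that. Section 10 states no such restriction, and the Phase 6 extraction form on care engagement makes records of all 150 the likelier source, although this remains an inference.

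**Conclusion.** A minor inconsistency, with an outcome source left unstated. Aim 4 and Phase 6 define different record-review groups as soon as one selected woman misses the survey, and section 10 gives neither source nor denominator for retention in PMTCT. The bias is nil if Phase 6 is followed with records as the source, or if completion is unrelated to retention.

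Otherwise its size is unknown. Under the assumed 60% versus 80%, with completion equal across arms, the shift runs from −1.4 to −9.5 points, always below the roughly 25-point sampling half-width. Completion that differs by arm could move the difference either way. It would be wrong to read these figures as a forecast, or as showing that selection would dominate the pilot's findings. They show only why the text should settle the matter before the estimates are passed to the R01.

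**What to change.** 1. **Aim 4:** change the sentence to match Phase 6, so that records are abstracted for all HIV-positive randomised women and the 100 selected HIV-negative women, whether or not they complete the 3-month survey.
2. **Section 10:** state that retention in PMTCT is taken from medical records and analysed by assigned arm, with all HIV-positive randomised women in the denominator. Section 10 also gives no definition or time window for this outcome; the same line is the natural place for them.

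The cost is one sentence in Aim 4 and about two lines in section 10. No chart reviews are added to the 150 that Phase 6 already plans. Compared with a literal reading of Aim 4, the wording keeps in about 5 to 14 of the 50 HIV-positive women under the three assumed patterns that produce bias. The reported retention figure may be less favourable.
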